9.3.6 Pharmacodynamic Analyses

All PD parameters will be presented by listings and descriptive summary statistics separately by treatment group.

All analyses of PD and exploratory biomarkers will be based on the safety analysis population (Section [9.2](#)).

For the analysis of PD biomarkers, the primary evaluation will be based on the observed change from baseline. Both actual values and estimated parameters will be presented in summary tables and graphically as deemed appropriate.

To assess predictability of a biomarker, the association between clinical outcome and the biomarker level or changes thereof will be explored.

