	as measured by the European Organisation for Research and Treatment of Cancer (EORTC) Quality-of-life questionnaire (QLQ)-C30, IL97, and OES-18, defined as an improvement of at least 10 points
To investigate the pharmacokinetics (PK) of RO7247669 and nivolumab.	
 Serum concentrations, PK profiles and parameters for RO7121661, RO7247669, and nivolumab
To evaluate the immune response after administration of RO7247669 and nivolumab.	
 Incidence and titer of RO7121661, RO7247669 or nivolumab anti-drug antibodies (ADAs) during the study relative to the prevalence of ADA at baseline
To assess treatment-induced pharmacodynamic changes (PD Biomarkers) in peripheral blood and tumor microenvironment	
 Changes from baseline in the phenotype and activation status (CD4/CD8 HLA-DR+Ki67+) of T-cell subsets in the peripheral blood Changes from baseline such as CD8 T-cell infiltration, proliferation (CD8+Ki67+) in the tumor microenvironment
To assess baseline characteristics in the tumor microenvironment as predictive biomarkers of response	
 Baseline PDL1, CD8+PD1+, CD8+TIM3+, and CD8+LAG3+ expression in the tumor microenvironment
Exploratory	
To evaluate the efficacy of RO7121661 and RO7247669 compared with nivolumab.	
 Changes in disease-related symptoms, function, and health-related quality of life as measured by the EORTC QLQ-C30, IL-97, and OES-18 Proportion of responses on the PGI-CI and PGI-S
To evaluate the efficacy of RO7121661 compared with nivolumab.	
 OS, defined as the time from randomization to death from any cause ORR, DCR, DoR, PFS as defined above according to RECIST v1.1 Proportion of participants reporting clinically meaningful improvement in global health status/quality of life, emotional functioning, social functioning and dysphagia as measured by the EORTC QLQ-C30, IL97, and OES-18, defined as an improvement of at least 10 points
To investigate the PK of RO7121661	
 Serum concentrations, PK profiles and parameters for RO7121661.
To evaluate the immune response after administration of RO7121661	
 Incidence and titer of RO7121661 ADAs during the study relative to the prevalence of ADA at baseline

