4.1.6 Rationale for Biomarker Assessments

The main hypothesis is that additional checkpoint blockade via PD1-TIM3 or PD1-LAG3 will re-invigorate exhausted T cells and lead to an increase in CD8 T-cell infiltration and proliferation in the tumor microenvironment. As such, treatment-induced biomarker exploration will focus on changes from baseline associated with anti-PD1-LAG3, anti-PD1-TIM3, and anti-PD1 therapy in both the tumor microenvironment and peripheral blood. In peripheral blood, serial blood sampling will also be done to assess kinetic changes in immune cellular profiles and selected cytokines, and examined for association with treatment with RO7121661, RO7247669, and nivolumab. Samples for pharmacodynamics (PD) and biomarker research will be collected as described in the SoAs (Section 1.3), and with respect to analyses and samples detailed in Section 8.7 and Section 8.8.

To explore predictive markers of response for RO7247669 or RO7121661, the initial hypothesis focuses on association of response with baseline PDL1, CD8+TIM3+, CD8+LAG3+, and PD1 expression. Other exploratory biomarkers considered to identify potential predictive markers also include assessing baseline immune-cell subsets/effector gene signatures in the peripheral blood and tumor microenvironment, oral, and gut microbiomes, or other soluble markers (such as bTMB, ctDNA, etc.).

Additional biomarkers may be measured if initial data lead to a strong scientific rationale for these measurements.

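### The pharmacodynamic hypothesis concerns what LAG3 blockade adds to PD1 blockade, but Section 9.3.6 specifies only change from baseline by arm and no RO7247669-minus-nivolumab estimate

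*Combined protocol and SAP*

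**What the plan says.** Section 4.1.6 (Rationale for Biomarker Assessments) gives the hypothesis: "The main hypothesis is that additional checkpoint blockade via PD1-TIM3 or PD1-LAG3 will re-invigorate exhausted T cells". The expected result is more CD8 T-cell infiltration and proliferation in the tumor. The same section says that "treatment-induced biomarker exploration will focus on changes from baseline associated with anti-PD1-LAG3, anti-PD1-TIM3, and anti-PD1 therapy", and that blood profiles and cytokines will be "examined for association with treatment with RO7121661, RO7247669, and nivolumab".

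Table 5 in Section 3 lists the secondary objective as "To assess treatment-induced pharmacodynamic changes (PD Biomarkers) in peripheral blood and tumor microenvironment". Its tumor endpoint is "Changes from baseline such as CD8 T-cell infiltration, proliferation (CD8+Ki67+) in the tumor microenvironment". The safety and efficacy objectives in that table are worded as comparisons with nivolumab; this one is not.

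Section 9.3.6 (Pharmacodynamic Analyses) says: "All PD parameters will be presented by listings and descriptive summary statistics separately by treatment group". It then says: "For the analysis of PD biomarkers, the primary evaluation will be based on the observed change from baseline". It uses the safety population and gives no model, contrast, interval, significance level or success rule. Section 9.3 leaves further detail to a separate technical document, which is not part of the text reviewed here.

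**The concern.** RO7247669 and nivolumab both block PD1. The biological claim that separates them is that LAG3 blockade adds something, so the quantity of interest is a difference between randomised arms. A change from baseline in the RO7247669 arm combines three things: any effect of PD1 blockade, any drift over time such as recovery after chemotherapy, and any LAG3 contribution. Nothing within that arm can separate them.

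The trial has what is needed to separate them: a randomised PD1-only arm, one sampling schedule for all arms (Table 2) and a pre-dose Cycle 1 blood sample. At stake is whether a secondary objective yields an estimate, with its uncertainty, of what the second target contributes. Without one, readers must judge the difference by eye from separate summaries. A rise in the RO7247669 arm could then be taken as evidence for the mechanism when nivolumab does the same.

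**Working it through.** The plan states no PD sample size, effect size or error rate, so there is no figure to reproduce. The check has two parts.

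**1. The sections side by side**

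| Item | What it refers to |
|---|---|
| Hypothesis (4.1.6) | Effect of the second checkpoint on top of PD1: a between-arm quantity |
| Secondary objective and endpoints (Table 5) | Change from baseline; no comparator named |
| Primary PD evaluation (9.3.6) | Change from baseline, described by arm |
| Blood kinetics (4.1.6) | Association with treatment; no method or contrast given |

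Elsewhere the plan does specify contrasts. In Table 9, ORR and PRO improvement have between-arm differences with 95% CIs, and PFS has a stratified log-rank test and hazard ratio. The PD section has no equivalent.

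**2. How far a within-arm change can mislead (illustration)**

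Assumptions, none from the documents: marker SD 1 at baseline and follow-up, correlation 0.6, 5% two-sided level, no LAG3 contribution, and the same true shift in both arms. Numbers of pairs per arm are 15, 30 and 85. The last is 255/3, the original planned total split equally; the allocation ratio and the revised size are redacted.

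*Within-arm paired t-test.*
- SD of change = sqrt(2 × (1 − 0.6)) = sqrt(0.8) = 0.894.
- Non-centrality = (shift / 0.894) × sqrt(n).
- Shift 0.5: 2.17, 3.06 and 5.15 for n = 15, 30 and 85.
- Shift 0.25: 1.08, 1.53 and 2.58.

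*Baseline-adjusted (ANCOVA) arm contrast.*
- Residual SD = sqrt(1 − 0.6²) = 0.8.
- SE of the difference = 0.8 × sqrt(2/n) = 0.292, 0.207 and 0.123.
- Approximate 95% CI half-width = 1.96 × SE = 0.57, 0.41 and 0.24 SD.
- Non-centrality for a true added effect of 0.5 SD = 0.5 / SE = 1.71, 2.42 and 4.07.

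Results from 4000 simulated trials per setting (direct non-central t calculation agrees to within two percentage points):

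| Pairs per arm | Within-arm test significant, shared shift 0.25 SD | Same, shared shift 0.5 SD | Between-arm contrast significant, no added effect | Power of contrast, added 0.5 SD |
|---|---|---|---|---|
| 15 | 16% | 52% | about 5% | 37% |
| 30 | 31% | 84% | about 5% | 65% |
| 85 | 71% | over 99% | about 5% | 98% |

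A second calculation by normal approximation, with the shared change d in units of the SD of change, used P = Φ(d × sqrt(n) − 1.96). It gave 16% to over 99% for n = 10 to 40 and d = 0.3 to 0.8, against 5% for the between-arm contrast. The pattern does not depend on the correlation chosen.

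**The case against.** The strongest reply is that the plan tests nothing here. Section 9.3.6 describes change from baseline and sets no null, error rate or success rule, so the rejection rates above belong to a test the plan does not contain. That is right: they show what a within-arm change can and cannot tell a reader, and are not an error rate of the plan.

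A reader might also infer that the sponsor will count any RO7247669 change as confirmation of the mechanism. The documents do not support this. Summaries by treatment group include nivolumab, so a shared change would be seen, and Section 4.1.6 mentions association with treatment for blood markers. Nor does the text show that no contrast will ever be run, since the separate analysis document may add one. Regression to the mean is not a persuasive source of spurious change either, because no eligibility criterion selects on these markers.

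The Table 5 objective, taken alone, does match its analysis: both concern change from baseline. The increment appears only in the rationale. Finally, fresh biopsies are optional (Section 8.8.2), so a tumor contrast would rest on consenting participants, possibly few. Randomisation does not fully protect such a subset.

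These points limit the concern without removing it. Tables side by side give neither an estimate nor an interval for the difference, and noting that one arm's change is significant while the other's is not is no valid substitute. The biopsy limitation does not apply to the mandatory blood samples (Section 8.8.1).

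**Conclusion.** The point holds in a limited form. The hypothesis in Section 4.1.6 is an increment over PD1 blockade. The stated primary PD evaluation does not estimate that increment, and the protocol specifies no RO7247669-minus-nivolumab difference or interval for these markers. A within-arm change that nivolumab shares could be misread as support. It would be too strong to say that it will be, or that the analysis will usually appear to confirm the mechanism: with a shared shift of 0.25 SD and 15 or 30 pairs, even a formal within-arm test would be significant in only 16% or 31% of trials.

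The size of the problem cannot be fixed from the documents; the figures rest on assumed SD, correlation, shift and number of pairs. This is a secondary, descriptive analysis in a study that calls itself hypothesis-generating, and the overall survival conclusion is unaffected. The change is worth making because it is cheap and supplies the missing estimate.

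**What to change.** In Section 9.3.6, and consistently in the separate analysis document:

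- Name the RO7247669-minus-nivolumab difference in the post-baseline marker, adjusted for its baseline value, with a 95% CI, as the estimate addressing the Section 4.1.6 hypothesis. Use the log scale for skewed markers. Add the stratification factors as covariates where the number of pairs allows.
- Keep within-arm change from baseline as a descriptive display, and show the number of paired samples in each arm.
- Label the tumor contrast exploratory, because it rests on an optional-biopsy subset.
- Compare RO7121661 only with nivolumab participants randomised concurrently, also as exploratory.

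The cost is a few sentences and a few model-based tables, with no new samples, visits or participants. The tumor interval may be wide: about ±0.57 SD with 15 pairs per arm under the assumptions above. Reporting that width is more informative than leaving the difference unestimated.

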9.3.7 Pharmacokinetic/Pharmacodynamic Relationships

Exploratory graphical analyses of exposure-effect relationships may be produced for selected efficacy, PD, and/or safety measurements if appropriate. A PK/PD modelling approach may be considered in order to further explore the exposure-response relationship of selected response variables. Data will be explored using linear and/or exponential models, as appropriate, in non-linear mixed effect modelling software. Additional PK analyses will be conducted as appropriate.

9.3.8 Other Analyses

Completion rates and reasons for missing data will be summarized for the QLQ-C30, QLQ-OES18, IL97, PGI-CI, and PGI-S at each treatment cycle by treatment arm and within the ITT population.

Visit mean summary and change from baseline analyses will be performed for all scales of the QLQ-C30, QLQ-OES18, and IL97. Summary statistics (e.g., number of participants, mean, standard deviation, median, minimum, maximum, 95% CI) of linearly transformed scores (per the EORTC scoring manual) will be calculated at all assessment time-points for each treatment arm. These analyses will be performed in the PRO-evaluable population.

Summary statistics (e.g., number of participants, proportions) will be calculated for the PGI-CI and PGI-S in the PRO-evaluable population.

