- b) As exception, a mandatory baseline fresh biopsy is required to be collected in case no suitable archival tissue sample is available to assess the PD-L1 positivity of a participant's tumor (see Section 5.1)
- c) An additional sample should be taken upon occurrence of colitis, as assessed and confirmed by the Investigator.
- d) Samples for RBR DNA saliva will be collected on Day 1 from all participants who signed RBR ICF prior to study drug infusion. If the RBR DNA saliva sample is not collected during the scheduled visit, it may be collected at any time during the conduct of the clinical study.

Table 3 Schedule of Assessment for Patient-Reported Outcomes

Cycle length 14 days	Day (D)	QLQ-C30 ^a	QLQ-IL97 ^a	QLQ-OES18 ^a	PGI-CI ^a	PGI-S ^a	PRO-CTCAE ^a
Cycle 1	Day 1	x	x	x		x	x
	Day 8 (± 1 day)						x ^b
Cycle 2	Day 1		x	x			x
	Day 8 (± 1 day)						x ^b
Cycle 3	Day 1		x	x	x	x	x
	Day 8 (± 1 day)						x ^b
Cycle 4	Day 1	x		x			x
	Day 8 (± 1 day)						x ^b
Cycle 5	Day 1		x	x			x
	Day 8 ± 1 day)						x ^b
Cycle 6	Day 1		x	x	x	x	x
Cycle 7	Day 1	x		x			x
Cycle 8	Day 1		x	x			x
Cycle 9	Day 1		x	x	x	x	x
Subsequent cycles	Day 1	C10 and then every 6 cycles		x	C12 and then every 6 cycles	C12 and then every 6 cycles	x
Treatment Discontinuation	≤ 30 Days after Last Dose	x		x	x	x	x
Follow-up	90 (±7 days) post last dose, then every 3 months (±2 weeks)	Every 3 months during the 1st year post discontinuation ^b		Every 3 months during the 1st year post discontinuation ^b			At 1st follow-up only ^b

Abbreviations: C = Cycle. PRO = Patient-reported outcome.

- a) All PRO instruments are required to be administered before the participant receives any information on disease status, prior to the performance of non-PRO assessments, and prior to the administration of study treatment, unless otherwise specified. In scenarios where assessments (e.g., blood draws) are done at a different location than the one providing treatment or when they are done on a different day than study treatment administration, laboratory assessments can be completed before the completion of PRO instruments as long as results have not been discussed with participants.
- b) On days where no site visit is planned, remote completion of PROs is accepted.

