8.1.2.2 Description of Clinical Outcome Assessment Instruments

EORTC QLQ-C30

The QLQ-C30 is a validated and reliable self-reported measure ([Aaronson et al. 1993](#); [Fitzsimmons et al. 1999](#); [Appendix 8](#)).

It consists of 30 questions that assess five aspects of patient functioning (physical, emotional, role, cognitive, and social), global health status and quality of life (GHS/QoL), and nine symptoms (fatigue, nausea and vomiting, pain, dyspnea, insomnia, appetite loss, constipation, diarrhea, and financial difficulties) with a recall period of the previous week. The functioning and symptoms items are scored on a 4-point scale that ranges from "not at all" to "very much," and the GHS/QoL items are scored on a 7-point scale that ranges from "very poor" to "excellent."

EORTC QLQ-OES18

The QLQ-OES18 is a validated and reliable self-reported measure that serves as a modular supplement to the QLQ-C30 for use in patients with esophageal cancer ([Blazeby et al. 2003](#); [Appendix 9](#)). It consists of 18 questions that assess four scales and six single items with a recall period of the previous week. The scoring for the QLQ-OES18 follows that of the QLQ-C30.

EORTC IL97

The IL97 is a reduced version of the QLQ-C30 that was created specifically for this study from the [EORTC Quality of Life Group Item Library](#). It consists of 17 questions that assess two aspects of patient functioning (emotional and social), GHS/QoL, and six symptoms (fatigue, nausea, vomiting, pain, appetite loss, and diarrhea) with a recall period of the previous week ([Appendix 10](#)). The scoring for the IL97 follows that of the QLQ-C30.

PGI-CI

The PGI-CI is a two-item, self-reported measure used to assess patients' impression about changes to their overall health because of their cancer and the associated importance compared with when they began the study ([Appendix 11](#)). In the first item, the PGI-CI uses a 7-point response scale that ranges from "very much worse" to "very much improved" (adapted from [Guy et al. 1976](#)). In the second item, the PGI-CI uses a 3-point response scale ("yes," "no," and "not applicable") for patients to indicate if the change they experienced (and reported in the first item) was important to them.

PGI-S

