9.2 POPULATIONS FOR ANALYSES

For purposes of analysis, the following populations are defined in [Table 8](#).

Table 8 Analysis Populations

Population	Description
Intent-to-treat	All randomized participants will be included in the intent-to-treat population.
Safety	All participants randomized to study treatment and who received any amount of the study treatment, whether prematurely withdrawn from the study or not, will be included in the safety analysis.
Pharmacokinetic	All participants who have received at least one dose of study treatment and who have data from at least one post-dose sample will be included in the PK analysis population. Participants will be excluded from the PK analysis population if they significantly violate the inclusion or exclusion criteria, deviate significantly from the protocol, or if data are unavailable or incomplete which may influence the PK analysis. Excluded cases will be documented together with the reason for exclusion. All decisions on exclusions from the analysis will be made prior to database closure.
Immunogenicity	Participants who had at least one pre-dose or at least one post-dose ADA assessment will be included and analyzed according to the treatment they actually received or were allocated to receive. The relationship between ADA status and safety, efficacy, PK, and biomarker endpoints will be analyzed and reported descriptively via subgroup analyses.
PRO-evaluable population	All randomized participants with a non-missing baseline assessment and at least one post-baseline assessment for the respective PRO will be included in the PRO-evaluable population.

ADA = Anti-drug antibody; PK = Pharmacokinetic; PRO = Patient-reported outcome.

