9.3.1 Demographics and Baseline Characteristics

Study enrollment, study drug administration, reasons for study drug discontinuation, and reasons for discontinuation from the study will be summarized by treatment arm. Major protocol deviations, including major deviations with regard to the inclusion and exclusion criteria, will be summarized by treatment arm.

Demographic (including age, sex, and self-reported race/ethnicity) and baseline disease characteristics (e.g., ECOG Performance Status) will be summarized overall and by treatment arm.

Descriptive statistics (mean, median, standard deviation, and range) will be presented for continuous data, and frequencies and percentages will be presented for categorical data, as appropriate.

Baseline measurements are the last available data obtained prior to the participant receiving the study treatment.

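### The PGI-CI summaries are assigned to an analysis set that requires a baseline PGI-CI form, which is never scheduled, so that set is empty as written (minor)

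*Combined protocol and SAP*

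**What the plan says.** Four parts of the protocol bear on this.

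- **Endpoint.** Table 5 (Section 3) lists "Proportion of responses on the PGI-CI and PGI-S" under an exploratory objective comparing the efficacy of both experimental arms with nivolumab.
- **Analysis set.** Section 9.3.8 says: "Summary statistics (e.g., number of participants, proportions) will be calculated for the PGI-CI and PGI-S in the PRO-evaluable population". The PRO-evaluable row of Table 8 reads: "All randomized participants with a non-missing baseline assessment and at least one post-baseline assessment for the respective PRO will be included". Section 9.3.1 defines baseline: "Baseline measurements are the last available data obtained prior to the participant receiving the study treatment".
- **Instrument.** Section 8.1.2.2 describes the PGI-CI as recording patients' impression of "changes to their overall health because of their cancer and the associated importance compared with when they began the study". It is a change question by construction.
- **Schedule.** In Table 3 (Section 1.3) the first row is "Cycle 1 Day 1 x x x x x": five marks across six instrument columns, with the empty cell under the PGI-CI. The PGI-CI is marked at Cycles 3, 6 and 9, then "C12 and then every 6 cycles", and at treatment discontinuation.

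**The concern.** The population rule was written for instruments that are scored as a change from baseline, and it suits those. Section 9.3.8 applies the same rule to an instrument that measures change directly and has no baseline form. A programmer who follows Table 8 literally obtains no participants for the PGI-CI.

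At stake is one exploratory, descriptive output. Because that output is a proportion, its denominator is part of the result. Plausible substitutes (anyone with a post-baseline PGI-CI, anyone with a baseline on some other PRO, or the ITT population) would give different denominators, and the protocol does not say which to use.

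**Working it through.** No sample size, power or error-rate figure is involved, and the plan states no figure to reproduce. The check is to apply the Table 8 rule to the Table 3 schedule, one instrument at a time.

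**Rule.** For instrument *k*, evaluable set = (randomised with at least one baseline form of *k*) ∩ (randomised with at least one post-baseline form of *k*). By Section 9.3.1, a baseline form is one obtained before study treatment.

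**Sources of a pre-treatment form.** Table 1 refers all PRO timing to Table 3. Table 3 has no screening row, so Cycle 1 Day 1 is the only scheduled opportunity.

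| Instrument | Form at Cycle 1 Day 1 | First later form | Set under Table 8 |
|---|---|---|---|
| QLQ-C30 | yes | Cycle 4 Day 1 | not empty by design |
| IL97 | yes | Cycle 2 Day 1 | not empty by design |
| QLQ-OES18 | yes | Cycle 2 Day 1 | not empty by design |
| PGI-CI | **no** | Cycle 3 Day 1 | **empty** |
| PGI-S | yes | Cycle 3 Day 1 | not empty by design |
| PRO-CTCAE | yes | Cycle 1 Day 8 | not empty by design |

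(A treatment discontinuation visit can bring the first later form forward for a participant who stops early. It cannot supply a baseline.)

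**Timing of the first PGI-CI.** With 14-day cycles, Cycle 3 Day 1 falls on day 1 + 2 × 14 = 29. The form is completed before that day's infusion, but two doses have already been given, so it is not a baseline form under Section 9.3.1.

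**Result.** Scheduled baseline PGI-CI forms = 0. The first set in the intersection is empty, so the PGI-CI evaluable set is 0 in each arm. This does not depend on the number randomised, the allocation ratio or the completion rate, so nothing blacked out affects it.

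**Could the blank cell be a fault in reading the table?** The instrument itself says not. A question comparing health now with health at study start has nothing to compare before the first dose.

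**Could an unscheduled visit supply a baseline?** Section 8.11.5 allows unscheduled assessments only where clinically indicated. It creates no baseline form.

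**The case against.** Several points can be made on the other side.

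- **Grammar.** In the Table 8 sentence the phrase tying the assessment to the PRO in question could attach to the post-baseline assessment alone. The PGI-CI set would then not be empty. This is the less natural reading, and it leaves open which instrument's baseline is meant, so the text would need clarifying either way.
- **Deferred detail.** Section 9.3 says a separate technical document will give more detail on the analyses. It may define the PGI-CI set properly. That possibility stands, but the protocol text has no exception, and a plan that departed from Table 8 would conflict with it.
- **Small consequence.** The endpoint is exploratory and the output is counts and proportions, with no test or model. The data are collected on schedule. Section 9.3.8 summarises PGI-CI completion rates and reasons for missing data in the ITT population, so those tables survive. All of this stands and sets the grading.

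A reader might also infer two stronger consequences, which the documents do not support.

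- *That the work on what size of change matters to patients loses its anchor.* Section 4.1.7 names five measures jointly for that purpose (QLQ-C30, OES-18, IL97, PGI-CI and PGI-S) and does not single out the PGI-CI. No threshold derivation in Section 9.3 is tied to the PRO-evaluable set, the secondary PRO endpoint already fixes its threshold at 10 points, and the PGI-S remains available with a Cycle 1 Day 1 form.
- *That a replacement set would be picked after the results are seen.* Nothing shows this. The separate plan could settle it beforehand.

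**Conclusion.** The contradiction between Section 9.3.8, Table 8 and Table 3 is real. Read naturally, the PGI-CI analysis set has 0 participants in every arm, and the planned summary cannot be produced as written. This rests on reading the baseline condition instrument by instrument and on Table 3 being the full PRO schedule, as Table 1 indicates.

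The fault lies in the population definition, not in the design or the data collection: leaving the PGI-CI out at Cycle 1 Day 1 is sensible. It would be wrong to conclude that the endpoint's data are lost or that any main conclusion of the trial is at risk. Overall survival, the secondary endpoints, the PGI-S and the ITT completion tables are unaffected. Severity: minor.

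**What to change.** Add one sentence to the PRO-evaluable row of Table 8:

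> For the PGI-CI, which has no baseline by design, the PRO-evaluable population is all randomized participants with at least one post-baseline PGI-CI assessment.

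Leave the rule unchanged for the QLQ-C30, IL97, QLQ-OES18, PGI-S and PRO-CTCAE, and carry the same sentence into the separate analysis plan so that the two documents agree. The set would then be everyone with a PGI-CI form from Cycle 3 Day 1 onward or from the treatment discontinuation visit. Its size cannot be computed in advance because the documents give no completion rate.

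The cost is one sentence in each document, with no new data, visits or forms.
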